*In vitro* evaluation showed that brensocatib is not a significant inhibitor for CYP isozymes ( $IC_{50} > 30 \mu M$  for CYP1A2, 2A6, 2B6, 2C8, 2C9, 2C19, 2E1, and 3A4/5) or a significant inducer for CYP1A2, 2B6, and 3A4. In addition, it is not a significant inhibitor of transporters, including Pgp, BCRP, OATPs, OATs, OCTs, and MATEs ( $IC_{50} > 11 \mu M$ ). Therefore, at a clinically relevant concentration range ( $\leq 1 \mu M$ ), drug-drug interactions between brensocatib and CYPs and transporters modulators are not expected.

In a Phase 1 study in healthy volunteers (N=81 male participants), who were randomized to receive: (a) single doses of placebo or brensocatib (5, 15, 35, 50, or 65 mg), or (b) multiple doses of placebo or brensocatib (10, 25, 40 mg QD), daily dosing of brensocatib led to an exposure-related reduction in NE activity with a delayed onset of effect consistent with neutrophil maturation rates (Palmer et al., 2018). In the presence of potent CYP3A4 and Pgp inhibitors (verapamil 240 mg QD or itraconazole 200 mg BID), brensocatib  $C_{max}$  and AUC were altered slightly (14%-32% for AUC and -40%-53% for  $C_{max}$ ). The impact of the CYP3A4 and Pgp inhibitors on brensocatib exposure are considered not clinically significant since the altered  $C_{max}$  and AUC were similar to the range of inter-participant variability when brensocatib is dosed alone (ca. 20%-50%). Food intake (high-fat meal) showed a minor effect on brensocatib AUC (<10% reduction) but moderately delayed the oral absorption ( $t_{max}$  increased by 0-3 hours and  $C_{max}$  decreased by  $\leq 35\%$ ). The elimination  $t_{1/2}$  of brensocatib in healthy participants was 20-30 hours.

In the Phase 2b Study INS1007-201, a total of 256 participants with NCFBE who had at least 2 PEs in the previous year received brensocatic 10 mg QD (N=82), brensocatic 25 mg QD (N=87), or placebo (N=87). Brensocatic treatment prolonged the time to the first PE as compared with placebo ( $P = 0.03$  and  $0.04$  for brensocatic 10 mg vs placebo and brensocatic 25 mg vs placebo, respectively). The adjusted hazard ratio for exacerbation (brensocatic versus placebo) was  $0.58$  (95% CI:  $0.35 - 0.95$ ;  $P = 0.03$ ) in the 10 mg group and  $0.62$  (95% CI:  $0.38 - 0.99$ ;  $P = 0.046$ ) in the 25 mg group. Sputum NE activity was reduced from Baseline over the 24-week treatment period for both doses of brensocatic ([Chalmers et al., 2020](#)).

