3. STUDY OBJECTIVES AND ESTIMANDS

3.1. Primary Objectives and Estimands: Pharmacokinetics and Safety

Pharmacokinetic Objective(s)	
To evaluate the pharmacokinetics (PK) of brensocatic in participants with cystic fibrosis (CF) following once daily (QD) oral administration of study drug	
Population	Participants with CF defined by the inclusion and exclusion criteria of the CSP who received brensocatic
Treatment Regimen	1 tablet QD of brensocatic (actual treatment)
Endpoints	C_{max} , t_{max} , AUC_{0-24} , and $t_{1/2}$ on Day 1 and Day 28
Population Level Summary	Mean brensocatic dose levels for C_{max} , AUC_{0-24} , and $t_{1/2}$, median for t_{max}
Intercurrent Event (ICE)	
 Early discontinuation from brensocatic for any reason Not on stable cystic fibrosis transmembrane conductance regulator (CFTR) modulators for participants on modulators
Strategy	
For the first ICE, the While-On-Treatment strategy (including up to Day 35 follow-up period) will be applied.
 
For the second ICE, the Treatment Policy strategy will be used.

C_{max} = maximum plasma concentration, t_{max} = time to maximum plasma concentration, AUC_{0-24} = area under the concentration-time curve from time 0 to 24 hours post-dose, $t_{1/2}$ = elimination half-life.

Safety Objective(s)	
To evaluate the safety of brensocatic compared to placebo in participants with CF	
Population	Participants with CF defined by the inclusion and exclusion criteria of the CSP
Treatment Regimen	1 tablet QD of brensocatic or placebo (actual treatment)
Endpoints	Participant reported treatment-emergent adverse event (TEAE) and type of TEAE
Population Level Summary	Number and percentage of participants with each type of TEAEs and number of TEAEs
ICE	
 Early discontinuation from randomized investigational product (IP) for any reason
Strategy	The While-On-Treatment strategy (including the 28-days follow-up) will be applied.

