11. PHARMACOKINETICS

Individual PK parameters of brensocatic will be determined by non-compartmental analysis (NCA) using Phoenix[®] WinNonlin[®] (WNL) version 8.2 or later (Certara L.P, Princeton, New Jersey). PK outputs will be prepared using SAS Version 9.4 or higher (SAS Institute, Inc., Cary, North Carolina). The primary PK endpoints are brensocatic C_{max} , t_{max} , and AUC_{0-24} after single dose administration on Day 1; and C_{max} , t_{max} , AUC_{0-24} , and $t_{1/2}$ after multiple dose administration on Day 28. Brensocatic plasma concentrations and PK parameters, including the ones that are not included in the primary endpoint, will be summarized as described in [Section 7.1](#). Statistical summary tables and mean plasma concentration by time figures will be presented based on the PK Analysis Set. Brensocatic plasma concentration by time figures for individual participants and listings will be based on the Safety Analysis Set. PK parameters will be listed for the PK Analysis Set.

Strategies for ICEs as outlined in [Section 3.1](#), [3.2](#), and [7.2](#) will be applied.

If calculable, the following PK parameters listed in [Table 5](#): will be determined for brensocatic in plasma following single oral dose administration (Day 1).

Table 5: Plasma PK Parameters After Single Dose Administration or First Dose Administration of Multiple Dose Study

Parameter	WNL Name	CDISC Name	Definition
C_{max}	Cmax	CMAx	Maximum observed plasma concentration
t_{max}	Tmax	TMAx	Time to C_{max}
t_{last}	Tlast	TLST	Time of the last measurable (positive) concentration
AUC_{0-24}	AUC0_24	AUC24	AUC from time T1=0 to T2=24 hours
AUC_{last}	AUClast	AUCLST	AUC from time T1=0 to T2=the last timepoint with measurable concentration

CDISC = Clinical Data Interchange Standards Consortium.

If calculable, the PK parameters listed in [Table 6](#) will be calculated for brensocatic in plasma following multiple oral dose administration after last dose administration (Day 28).

Reasons for PK parameters not calculable will be listed.

Table 6: Plasma PK Parameters after Multiple Dose Administration after Last Dose

Parameter	WNL Name	CDISC Name	Definition
C_{trough}	Ctrough	CTROUGH	Concentration at the end of a dosing interval [taken directly before next administration]; Obtained on Days 2, 14, 28 and 29

Parameter	WNL Name	CDISC Name	Definition
C_{\max}	Cmax	CMAx	Maximum observed plasma concentration in a dosing interval

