λ_z and $t_{1/2}$	
 The terminal phase first-order rate-constant (λ_z) will be estimated. A minimum number of three data points in the terminal phase will be used in calculating λ_z with the adjusted correlation coefficient (R^2 adjusted) ≥ 0.8. Otherwise, λ_z will be considered not calculable, and all the λ_z dependent parameters (i.e., $t_{1/2}$, CL/F, and Vd/F) will be flagged in listings and excluded accordingly from summary tables and statistical analysis of PK parameters. The reason for exclusion will be listed/footnoted in parameter listings. Unless otherwise determined by PK Scientist's best knowledge and judgment, the interval used to determine λ_z should be equal or greater than 1.5-fold the estimated $t_{1/2}$, and if less than 1.5-fold, λ_z will be flagged in listings and might be excluded (based on sponsor specific requirements) from summary tables and statistical analysis of PK parameters. All the derived parameters (i.e., $t_{1/2}$, CL/F, and Vd/F) may also be flagged in listings and excluded from statistical analysis of PK parameters. The reason for exclusion will be listed/footnoted in parameter listings. The $t_{1/2}$ will be calculated as follows: $t_{1/2} = \ln 2 / \lambda_z = 0.693 / \lambda_z.$
CL/F	
Following extravascular (e.g., oral) administration, apparent systemic clearance of parent drug following steady state administration will be calculated from:
 $CL/F = \frac{Dose}{AUC_{0-24}}$ 
The administered brensocatib dose will be used for the calculation.

V _d /F	
Volume of distribution at terminal phase following either intravascular or extravascular dosing after steady state administration may be calculated from:
 $V_d/F = \frac{Dose}{\lambda_z * AUC_{0-24}} = (CL/F) / \lambda_z$

Parameter	Guideline for Derivation
C_{av}	Average concentration at steady state (Day 28) will be calculated as $C_{av} = AUC_{0-24}/24$
R_{ac}	Accumulation ratio, calculated from comparison of single dose and steady state data: $R_{acAUC} = \text{Steady state } AUC_{0-24} / \text{Single dose } AUC_{0-24}$ $R_{acC_{max}} = \text{Steady state } C_{max} / \text{Single dose } C_{max}$

PK Parameters Listings:

PK parameters will be listed by participant. PK parameters that will be flagged and/or excluded from summary tables and statistical analyses of PK parameters will be flagged and footnoted with the reason for flagging/exclusion.

The Phoenix NCA core output will be provided as a Word document.

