13. CHANGES TO PROTOCOL-SPECIFIED ANALYSES

Currently, no changes from the protocol-specified analyses are planned.

A Screened Analysis Set was defined in [Section 6.1](#) in addition to the analysis sets defined in the CSP.

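### SAP Table 7 ties CL/F to the terminal slope although its formula does not use it, and the SAP contradicts itself on whether Day 1 half-life is a primary endpoint

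*SAP*

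**What the plan says.** **CL/F.** SAP Section 11.1.2, Table 7, has two rules for the terminal slope λz.

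- The first is mandatory. λz needs at least three terminal points and an adjusted R² of 0.8 or more. If it fails, λz counts as not calculable and half-life, "CL/F, and Vd/F) will be flagged in listings and excluded accordingly from summary tables and statistical analysis of PK parameters".
- The second is discretionary. The interval used for λz "should be equal or greater than 1.5-fold the estimated" half-life. If it is shorter, λz is flagged and might be excluded, and the same three derived parameters may be excluded with it. The PK scientist can override this rule.

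The CL/F row of the table says that "apparent systemic clearance of parent drug following steady state administration will be calculated from" dose divided by AUC0-24. The AUC∞ row adds the last quantifiable concentration divided by λz to AUClast. Neither rule names AUC∞.

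**Day 1 half-life.** Protocol Sections 1.1, 3, 8.3.2 and 9.4.2 list half-life among the primary PK endpoints for both days. SAP 3.1 also gives it "on Day 1 and Day 28". SAP Section 11 names Cmax, tmax and AUC0-24 "after single dose administration on Day 1; and" then adds half-life for Day 28 only. Table 5 (Day 1 parameters) has no half-life; Table 6 (Day 28) does. SAP Section 13 states: "Currently, no changes from the protocol-specified analyses are planned".

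**The concern.** The list of λz-dependent parameters does not match the formulas beside it. A participant with a complete Day 28 dosing interval has a valid CL/F, yet the rule removes it from the summaries because of a poor terminal fit that CL/F never uses. The protocol's dose rationale (Sections 2.2 and 4.3) is that people with CF may clear drug faster, so CL/F is a parameter that readers will look for. The cells are small, and SAP 7.1 gives no PK-parameter statistics below three values.

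On half-life, a primary endpoint is in one part of the SAP and absent from another, with no recorded decision. The clause in SAP Section 2 that gives the SAP precedence over the protocol cannot settle a disagreement inside the SAP.

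**Working it through.** The plan states no figure on this point, so there is none to reproduce. The check is algebra on Table 7 and an interval calculation.

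**1. Which parameters use λz (formulas from Table 7)**

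- t1/2 = ln 2 / λz: uses λz.
- Vd/F = Dose / (λz × AUC0-24): uses λz.
- AUC∞ = AUClast + Clast / λz: uses λz, not listed.
- CL/F = Dose / AUC0-24: does not use λz, but is listed.
- Cav = AUC0-24 / 24: does not use λz, and is kept.

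Since AUC0-24 = 24 × Cav, CL/F = Dose / (24 × Cav). The plan would keep Cav and exclude a quantity carrying the same information.

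**2. What exclusion does to the cells (Protocol Table 1; SAP 7.1)**

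Each dose has about 7 participants: 5 in the modulator stratum and 2 in the non-modulator stratum. Three exclusions in a stratum of 5 leave 5 − 3 = 2 values, and its CL/F summary disappears. At dose level it takes five (7 − 5 = 2). The non-modulator cell, at 2, is below three in any case.

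**3. Day 28 interval (Protocol 1.3.1)**

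The half-life "of brensocatib in healthy participants was 20-30 hours" (Protocol 2.1); the documents give no CF value.

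- With the 168 h sample quantifiable, 8 to 168 h is 160 h: 160/30 = 5.3 to 160/20 = 8.0 half-lives. The 1.5-fold guideline is met.
- From 24 h to 168 h is 144 h, so C168/C24 = 2^(−144/20) = 0.7% to 2^(−144/30) = 3.6%. Whether that is quantifiable depends on the LLOQ, which is not stated.
- Without the 168 h sample, the points at 4, 6, 8 and 24 h remain. Three points are available, so the mandatory rule can still be passed. The 1.5-fold guideline would not be met at 20 to 30 h.

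**4. Day 1 interval**

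The last Day 1 sample is at 24 h, or 25 h with the +1 h window.

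- Required: 1.5 × 20 = 30 h to 1.5 × 30 = 45 h.
- Available, counting generously from time 0: 24/30 = 0.80 to 25/20 = 1.25 half-lives.
- Last three samples only (6, 8 and 24 h): 18/30 = 0.6 to 18/20 = 0.9 half-lives.
- Longest estimated half-life that passes: 24/1.5 = 16.0 h; 25/1.5 = 16.7 h with the window; 18/1.5 = 12.0 h on the last three points.

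**5. How many individuals might pass on Day 1 (assumption, not in the documents)**

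Suppose individual half-lives are log-normal, with s = √ln(1 + CV²). A 1 to 24 h fit passes below 23/1.5 = 15.3 h, so the share is Φ(ln(15.33/GM)/s).

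| Geometric mean | CV 20% | CV 30% | CV 50% |
|---|---|---|---|
| 20 h | 9% | 18% | 29% |
| 25 h | 1% | 5% | 15% |
| 30 h | 0% | 1% | 8% |

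A minority could pass. A Day 1 half-life summary built on them would represent only the shortest half-lives.

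**The case against.** The strongest reply is that nothing the study depends on is lost. CL/F is neither primary nor secondary; the protocol synopsis lists it among additional parameters obtained when data permit. AUC0-24 is primary and no λz rule touches it. At a given dose, CL/F is dose over AUC0-24, and SAP 11.1.3 provides comparisons of dose-normalised AUC0-24 across doses and, if dose proportionality holds, between strata. Excluded CL/F values stay in the listings with a reason. All of this stands, so a reader who infers that clearance information is destroyed goes too far.

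A reader might also infer that a 168 h sample below quantification automatically removes CL/F, chiefly at low doses or in fast clearers. The documents do not support that. Such a sample does not by itself fail the mandatory rule, exclusion under the 1.5-fold guideline is optional, and without an LLOQ the pattern of loss cannot be stated.

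Nor is AUC∞ wrongly kept when λz is not calculable, since it then cannot be computed. The omission matters mainly under the discretionary rule, where a flagged λz could take CL/F out and leave AUC∞ in.

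On half-life, SAP Section 11 and Table 5 have already dropped Day 1, so the endpoint would not surface as a column of failed derivations. Protocol 8.3.2 qualifies its parameter list as applying where appropriate, and SAP Section 2 promises that differences from the protocol will be detailed in the CSR. That leaves the conflict between SAP 3.1 and Section 11, and the silence of Section 13.

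**Conclusion.** Both defects hold, and both are minor SAP corrections.

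First, Table 7 misclassifies CL/F. Exclusion is mandatory under the three-point, adjusted R² rule and optional under the 1.5-fold rule. The cost is valid values missing from CL/F summaries in cells of about 7 or 5; three losses empty the smaller one. The frequency cannot be estimated without the LLOQ and assay noise.

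Second, the SAP contradicts itself on Day 1 half-life and does not record the departure from the protocol. Omitting it, as Section 11 does, is sensible: at 20 to 30 h the guideline would not be met unless the individual estimate is about 16 h or less or the PK scientist overrides it. A reader might go further and say that Day 1 half-life can never be derived. That is not established, because 20 to 30 h comes from healthy participants and the guideline applies to each participant's own estimate.

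Neither defect changes AUC0-24, Cmax, tmax, the TEAE results or the dose-dependency model.

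**What to change.** Before database lock:

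- In both λz rules of SAP Table 7, replace the bracketed list of half-life, CL/F and Vd/F with half-life, Vd/F and AUC∞. Day 28 CL/F is then kept whenever AUC0-24 is available.
- In SAP 3.1, make half-life a Day 28 endpoint only, in line with Section 11 and Tables 5 and 6.
- In SAP Section 13, and later in the CSR, record that Day 1 half-life is not derived as the protocol lists it, and give the 24 h sampling limit as the reason.

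The cost is SAP wording and a matching change to the programming specification for CL/F. No data are affected, and no protocol amendment is needed to run the analysis.

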11.1.3. Assessment of Dose Proportionality

Analysis of dose dependency for brensocatic AUC_{0-24} , AUC_{last} , and C_{max} after single-dose administration and at steady state (Day 28) will be performed using a power law model². The logarithm of the PK parameter will be linearly related to the logarithm of the dose using a linear regression analysis in the following way:

$$\ln(PK) = \beta_0 + \beta_1 \cdot \ln(\text{dose}),$$

where $\ln(PK)$ represents the natural log transformed AUC_{0-24} , AUC_{last} , and C_{max} parameter and $\ln(\text{dose})$ represents the natural log transformed dose as fixed factor.

LS estimates of the slope of the regression and corresponding 90% CIs will be obtained.

Dose proportionality plots for C_{max} , AUC_{0-24} , and AUC_{last} at Day 1 (after single dose administration) and at Day 28 (after multiple dose administration): the natural log-transformed PK parameter versus natural log-transformed dose will be displayed with the fitted line from the power law model. The individual natural log-transformed data will be displayed around the fitted line. The CFTR modulator / non-modulator groups will be displayed on the same plot.

A categorical covariate for CFTR modulator stratum or separate analyses by stratum may be conducted if the C_{max} , AUC_{0-24} , and AUC_{last} values between strata are dissimilar, as assessed by visual inspection of the above dose proportionality plots for C_{max} , AUC_{0-24} , and AUC_{last} parameters. A clear separation of the individual data for CFTR modulator / non-modulator groups suggests dissimilarity in the PK profile between the two CFTR strata. Analyses will be repeated for brensocatic PK parameters after multiple-dose administration on Day 28.

In addition, pairwise comparisons of dose dependency among brensocatic dose levels may be performed based on dose-normalized C_{max} , AUC_{0-24} , and AUC_{last} separately for Day 1 and Day 28. An analysis of variance will be run with the natural-log transformed ratio of the PK parameter divided by the dose as dependent variable and the dose level as independent fixed effect. The LS means and LS mean difference will be back transformed to obtain the geometric means and ratio of geometric means along with corresponding 90% CI. If dose proportionality holds between the 2 dose levels being compared, the ratio of geometric means will be approximately 1.00.

If dose proportionality applies, data within stratum (CFTR modulator and non-modulator) will be pooled across dose levels. The log-transformed dose-adjusted C_{max} , AUC_{0-24} , and AUC_{last} for Day 1 and Day 28 will be used as dependent variable in an analysis of variance with the CFTR stratum as independent variable. The LS mean for the difference between strata with 90% CI will be estimated from the model. The estimate and lower and upper confidence limits will be back transformed by exponentiation. The back-transformed difference between the strata is the GM ratio of the strata.

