### 1.3.1. PK, PD, and ECG Sampling Schedule

Day	Timepoint (window)	PK a	PD b (sputum)	PD b (blood)	ECG c
Screening Period Days -28 to -1			X	X	X
Day 1	Pre-dose	X	X	X	X
	0.5 h (± 5 min)	X			
	1 h (± 5 min)	X			
	2 h (± 5 min)	X			X
	4 h (± 15 min)	X			
	6 h (± 15 min)	X			X
	8 h (± 15 min)	X			
Day 2	24 h (± 1 h)	X	X	X	
Day 14	Pre-dose	X	X	X	X
	2 h (± 5 min)	X			X
Day 28	Pre-dose	X	X	X	X
	0.5 h (± 5 min)	X			
	1 h (± 5 min)	X			
	2 h (± 5 min)	X			X
	4 h (± 15 min)	X			

Day	Timepoint (window)	PK a	PD b (sputum)	PD b (blood)	ECG c
	6 h (± 15 min)	X			X
	8 h (± 15 min)	X			
Day 29	24 h (± 1 h)	X	X	X	
Day 35	168 h (± 24 h)	X	X	X	
E/D		X	X	X	X

a PK Sample Collection: Day 1 (predose and at 0.5, 1, 2, 4, 6, 8, and 24 hours postdose [24-hour postdose collection is Day 2 predose collection]), Day 14 (predose and at 2 hour postdose), Day 28 (predose and at 0.5, 1, 2, 4, 6, 8, 24 (collected on Day 29), and 168 hours postdose (±24 hours; collected on Day 35). The collection windows will be up to 30 minutes prior to dosing for the predose sample, ±5 minutes for the 0.5, 1, and 2-hour samples, ±15 minutes for the 4-, 6-, and 8-hour samples, ± 1 hour for the 24-hour sample, and ± 24 hours for the 168-hour sample.

b PD Sample Collection: Includes collection of 1 sputum sample and 1 blood sample at Screening, and at predose on Days 1, 2, 14, 28, 29, and 35; in addition, at E/D Visit, if applicable (the defined pre- and post-dose PK sampling timepoint windows do not apply to PD sample collections). A 6 ml sample of blood should be collected at each timepoint.

c ECG: 12-lead ECG will be performed at Screening, on Day 1 (predose [0 hour], at 2 and 6 hours postdose), on Day 14 (predose and 2 hours postdose), on Day 28 (predose, and at 2 and 6 hours postdose), and at the E/D Visit, if applicable, at which only 1 ECG will be performed. The ECG must be conducted within a ±10-minute window relative to the PK sampling time. ECG should be collected in triplicates with 10 second recording each.

ECG = electrocardiogram, E/D = Early Discontinuation, h = hour, min = minute, PK = pharmacokinetic, PD = pharmacodynamic.

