3.2. Secondary Objective and Estimand: Pharmacokinetics

Pharmacokinetic Objective(s)	
To evaluate the dose-dependency of brensocatib exposure	
Population	Participants with CF defined by the inclusion and exclusion criteria of the CSP who received brensocatib
Treatment Regimen	1 tablet QD of brensocatib (actual treatment)
Endpoints	C_{max} , AUC_{0-24} , and AUC_{last} on Day 1 and Day 28
Population Level Summary	Slope from a statistical model (if data allow estimation based on a statistical model) or ratio of geometric means (GMs)
ICE	
 • Early discontinuation from brensocatib for any reason • Not on stable CFTR modulators for participants on-modulators
Strategy	
For the first ICE, the While-On-Treatment strategy (including up to Day 35 follow-up period) will be applied.
 
For the second ICE, the Treatment Policy strategy will be used.

C_{max} = maximum plasma concentration, AUC_{0-24} = area under the concentration-time curve from time 0 to 24 hours post-dose, AUC_{last} = area under the concentration-time curve from time 0 to the last timepoint with measurable concentration.

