C_{\min}	Cmin	CMIN	Minimum observed plasma concentration in a dosing interval
t_{\max}	Tmax	TMAX	Time to C_{\max}
t_{last}	Tlast	TLST	Time of the last measurable (positive) concentration
$t_{1/2}$	HL_Lambda_z	LAMZHL	Elimination half-life
λ_z	Lambda_z	LAMZ	Elimination rate constant
AUC_{0-24}	AUC0_24	AUC24	AUC from time T1=0 to T2=24 hours
AUC_{last}	AUClast	AUCLST	AUC from time T1= 0 to T2=the last timepoint with measurable concentration
AUC_{∞}	AUC ∞	AUCINF	AUC from time T1=0 to T2=infinity
CL/F	CLss_F	CLFTAU	Total clearance following oral administration
V_d/F	Vz_F	VZFTAU	Volume of distribution at terminal phase following oral administration
C_{av}	Cavg	CAVG	Average concentration over the dosing interval
$R_{\text{ac,AUC}}$	RacAUC*	ARAUC	Accumulation ratio calculated from AUC_{0-24} at steady state divided by AUC_{0-24} after single dosing
$R_{\text{ac,Cmax}}$	RacCmax*	ARCMAX	Accumulation ratio based on C_{\max} calculated from C_{\max} at steady state divided by C_{\max} after single dosing

* Obtained through additional calculations in WNL outside of NCA model.

11.1. Pharmacokinetic Analysis, Concentration, and Parameter Tables, Listings, and Figures, and Statistical Analysis of Pharmacokinetic Parameters for Final Analysis

Any anomalous PK plasma concentration values observed at pre-dose on Day 1 will be identified in the CSR and reported in listings. All pre-dose values (BLQ and any anomalous values) will be set to zero.

PK plasma concentrations that are collected outside the acceptable collection windows (Section 1.3.1, CSP) will be flagged in the listing with a footnote that these concentrations are excluded from the concentration summary.

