11.1.2. Pharmacokinetic Parameters

PK parameters will be calculated by NCA methods from the concentration-time data as specified in beginning of [Section 11](#) following these guidelines:

- Actual time from dose will be used in the calculation of all derived PK parameters, except when parameters are calculated for safety/dose escalation meetings when nominal times may be used.
- There will be no imputation of missing data.
- Handling of BLQ samples for derivation of plasma PK parameters after single and multiple dose administration:
 - BLQs for Day 1 at the beginning of a participant profile (i.e., pre-dose and leading BLQs) will be set to zero.
 - BLQs between evaluable concentrations (embedded BLQs), will be set to missing before the calculation of the PK parameters.
 - Terminal BLQs (trailing BLQs at the end of participant profile) will be set to missing.

Participants with partial data will be evaluated on a case-by-case basis to determine if sufficient data are available for reliable estimation of PK parameters. PK parameters will be estimated according to the guidelines presented in [Table 7](#):

Table 7: PK Parameter and Estimation

Parameter	Guideline for Derivation
C_{max} , C_{min} , t_{max} , C_{trough} , t_{last} ,	Obtained directly from the observed concentration-time data

Parameter	Guideline for Derivation
AUC_{last}	
The AUC from zero time (pre-dose) to the time of last quantifiable concentration will be calculated by a combination of linear and logarithmic trapezoidal methods. Unless specifically requested and justified, the linear up/log down trapezoidal method will be employed for all AUC calculations.
 
The AUC_{last} is the sum of areas up to the time of the last quantifiable sample:
 $AUC_{last} = \int_0^t C_{last} * dt$
AUC_{0-24}	
The AUC from zero time to the specific time x is the sum of areas up to the specific time x sample, where x=actual time at 24h:
 $AUC_{0-x} = \int_0^x Cx * dx$ 
If the PK sample at 24h is collected out of time window, AUC_{0-24} and its related parameters will be flagged in the listing but included in the analysis.

AUC_{∞}	
The area from zero time extrapolated to infinite time (AUC_{∞}) will be calculated as follows:
 $AUC_{\infty} = AUC_{0-last} + C_{last}/\lambda_z$ 
where C_{last} is the last observed quantifiable concentration.

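### Day 28 AUClast can end at 24 h in some participants and near 168 h in others, so its dose-dependency slope can exceed 1 even when exposure is exactly dose proportional

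*SAP*

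**What the plan says.** The dose-dependency objective is secondary. Its endpoints are Cmax, AUC0-24 and AUClast on Day 1 and Day 28 (Protocol 3; SAP 3.2). Protocol 9.4.3 and SAP 11.1.3 regress the log parameter on log dose, and the SAP states that this "after single-dose administration and at steady state (Day 28) will be performed using a power law model". SAP 11.1.3 also allows a dose-normalised pairwise analysis of variance. If proportionality holds, it pools doses within stratum and compares the strata on dose-adjusted Cmax, AUC0-24 and AUClast.

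Four rules fix the interval that Day 28 AUClast covers:

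- **Sampling (Protocol 1.3.1).** The tail of the Day 28 profile is "24 (collected on Day 29), and 168 hours postdose (±24 hours; collected on Day 35", with nothing between.
- **Definition (SAP 11, Table 6; SAP 11.1.2).** AUClast runs to "T2=the last timepoint with measurable concentration".
- **Values below the limit, and missing values (SAP 11.1.2).** "Terminal BLQs (trailing BLQs at the end of participant profile) will be set to missing", and "There will be no imputation of missing data".
- **Follow-up (SAP 3.2).** For early discontinuation, "the While-On-Treatment strategy (including up to Day 35 follow-up period) will be applied". Follow-up samples to Day 35 are thus within scope.

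No common end time, condition on tlast or sensitivity analysis is attached to the AUClast models.

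**The concern.** Taken together, these rules give the response variable two possible integration intervals. A participant whose 168 h sample is below the limit, or was not taken, contributes an area to 24 h. A participant with a quantifiable 168 h sample contributes an area to about 168 h, roughly twice as large.

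For a given half-life, the 168 h concentration is proportional to dose. Results below the limit will therefore fall mainly in the low-dose arm, which pulls that end of the regression down and steepens the slope. A missed Day 35 visit shortens the interval in the same way, but it has no evident link to dose, so it adds noise more than direction.

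At stake is the reading of one secondary slope, the matching pairwise ratios and, indirectly, the decision to pool doses. SAP 11.1.3 makes pooling conditional on proportionality but gives no criterion for it. It also does not say which parameter decides if AUC0-24 and AUClast disagree.

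**Working it through.** **Plan's own figure.** The only stated AUC precision is the 95% CI factor for a geometric mean, exp[t(0.975, n−1) × √ln(1+CV²) / √n]. For n = 7 and CV 30%: exp(2.447 × 0.2936 / 2.646) = 1.312. CV 40% and 50% give 1.428 and 1.548. All three match SAP Table 2. No slope, power or LLOQ figure is stated.

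**Inputs from the documents.** Half-life 20-30 h in healthy participants (Protocol 2.1); AUC at 65 mg QD of at most 10 µg·h/mL (Protocol 2.2); about 7 participants per active dose; gCV 30-50% (SAP 4.2).

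**Assumed.** LLOQ 0.1-50 ng/mL; the healthy-participant half-life applies in CF; exposure lies at the 65 mg bound and scales with dose; one compartment; absorption rate 1.5/h in the simulation.

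**Step 1: ratio of the two intervals.** At steady state with rapid absorption, AUC0-168 / AUC0-24 = (1 − e^(−168k)) / (1 − e^(−24k)), with k = ln 2 / half-life. This gives 1.766 (20 h), 2.038 (25 h) and 2.301 (30 h). Using the planned sampling times, linear-up/log-down integration and the assumed absorption rate, it is 1.79, 2.06 and 2.32.

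**Step 2: effect on the slope.** If a share s of each arm reaches 168 h, the slope bias is ln(ratio) × Σ(xc·s) / Σ(xc²), where xc is centred ln dose. For 10, 25 and 40 mg, xc = −0.768, 0.149, 0.619 and Σ(xc²) = 0.994.

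- Shares 0, 50%, 100%: (0.074 + 0.619) / 0.994 = 0.697. Times ln 1.766 = 0.568 or ln 2.301 = 0.833, the bias is 0.40 to 0.58.
- Shares 4/7, 6/7, 7/7: (−0.439 + 0.128 + 0.619) / 0.994 = 0.31. The bias is 0.18 to 0.26.
- All or none at every dose: the bias is 0.

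These shares are illustrations. For scale, the half-width of the SAP's 90% CI for the slope at gCV 30% is 1.729 × 0.2936 / √(7 × 0.994) = 0.19.

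**Step 3: link to an LLOQ.** C168/C24 = e^(−144k) = 0.7%, 1.8% and 3.6% for 20, 25 and 30 h. At the assumed exposure, typical C168 is 0.29-1.75 ng/mL at 10 mg and 1.1-7.0 ng/mL at 40 mg.

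I simulated 4,000 trials per setting with a true slope of 1.00, 7 participants per dose at 10, 25 and 40 mg, gCV 30% and half-life uniform on 20-30 h:

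| Assumed LLOQ (ng/mL) | Mean Day 28 AUClast slope | Trials with 90% CI wholly above 1 |
|---|---|---|
| 0.1 | 1.00 | 5% |
| 0.5 | 1.12 | 19% |
| 1 | 1.29 | 48% |
| 2 | 1.38 | 65% |
| 5 | 1.13 | 16% |
| 10 | 1.01 | 6% |
| 50 | 1.00 | 5% |

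The nominal figure in the last column is 5%. Monte Carlo error there is at most √(0.25/4000) = 0.8 percentage points. AUC0-24 from the same data gives slopes of about 1.00 and about 5% throughout. At gCV 50% the peak is 1.35 (37% of trials). With a 65 mg arm at gCV 30% it is 1.35 (86%), and a bias of about 0.05 remains at 10 ng/mL. Halving the exposure halves the LLOQ values in the table.

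**The case against.** The strongest reply is that nothing in the documents shows any 168 h sample will be below the limit. The LLOQ appears nowhere, and the 20-30 h half-life comes from healthy participants. Outside a band of LLOQ values everyone stops at the same time and there is no bias. This stands: a reader might infer that Day 28 AUClast will mix intervals, but the documents support only that it can.

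Second, the plan already holds a fixed-interval check. AUC0-24 and Cmax go through the same models, tlast is summarised and parameters are listed by participant. Of six slopes (three parameters, two days), one is affected. This limits the harm. But tlast is summarised only by n, median, minimum and maximum (SAP 7.1), which does not count how many stopped at 24 h, and no rule says which slope prevails.

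Third, the study tests no hypotheses and sets no acceptance limit for the slope. That is correct, and it means nothing shows that AUClast alone would decide pooling. Equally, nothing prevents it from influencing that decision.

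Two further readings are tempting but unsupported. One is that Day 1 and Day 28 AUClast are wrongly compared. Their intervals can differ, but no planned analysis compares them, and the accumulation ratios use AUC0-24 and Cmax. The other is that the stratum comparison is biased by dose. Planned allocation is 5:2 at every active dose, so a dose-dependent interval does not by itself confound stratum. It could enlarge a real exposure difference between strata.

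**Conclusion.** The point holds as a conditional weakness of the Day 28 AUClast analyses. The SAP's own rules let the integration interval depend on dose through assay sensitivity, and the bias from values below the limit is upward. It ranges from nil to a mean slope of about 1.4 under exact proportionality. At its largest it exceeds the 0.19 half-width of the slope's 90% CI.

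That range rests on the assumed LLOQ, exposure at the protocol's projected bound, a healthy-participant half-life and a one-compartment profile. The Day 1 analyses and the Day 28 AUC0-24 and Cmax analyses are unaffected. The matter is worth correcting because the endpoint is prespecified, the pooling rule names no deciding parameter and an unbiased alternative is already planned.

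**What to change.** In SAP 3.2 and 11.1.3, including the pooling and stratum step, base Day 28 dose-dependency conclusions, and the decision that proportionality holds, on AUC0-24 and Cmax. Report Day 28 AUClast descriptively, or as a supportive slope only. In either case, show by dose the number of participants with tlast of 24 h and of 168 h.

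Do not restrict the AUClast model to participants who share the same tlast. That keeps only high-exposure or slowly eliminating participants at low doses. Under the same simulation assumptions, restricting to tlast of 168 h gives mean slopes of about 0.94, 0.86 and 0.80 at LLOQs of 0.5, 1 and 2 ng/mL, so an upward bias becomes a downward one. Cutting AUClast at 24 h adds nothing, because it then essentially repeats AUC0-24.

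The cost is SAP wording and one small table, with no new data. The drawback is that AUClast is a protocol secondary endpoint with a power model specified in Protocol 9.4.3. Demoting it departs from the protocol and must be recorded in SAP Section 13, which now says that no changes to the protocol-specified analyses are planned.
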